**Table 12–3: Required investigations and follow-up for PDILI**

Laboratory value		Symptoms a of hepatitis or hypersensitivity	Immediate		Follow up	
ALT or AST	Total bilirubin		Consultation requirements	Actions	Testing	Evaluation
						
 
If ALT or AST remains <math>\geq 5</math>xULN after second re-test, immediate IMP discontinuation required.
 
 
Continue to monitor until values normalize, stabilize, or return to within baseline values.e

ALP=alkaline phosphatase; ALT=alanine aminotransferase; ASAP=as soon as possible; AST=aspartate aminotransferase; HCP=healthcare practitioner; IMP=investigational medicinal product; NA=not applicable; PDILI=potential drug-induced liver injury; ULN=upper limit of normal

a Hepatitis symptoms include fatigue, nausea, vomiting, and right upper quadrant pain or tenderness; hypersensitivity symptoms include eosinophilia (>5%), rash, and fever (without clear alternative cause).

b If the subject also has  $\geq 2$ xULN ALP, the possibility of an indication of biliary obstruction should be discussed with the Medical Monitor.

c Details provided in [Section 12.2.1.1](#). The local hepatologist is the expert usually consulted by the treating physician for assessment and management of potential hepatic disease. This would usually be a hepatologist but may be a gastroenterologist.

d Details are provided in [Section 12.2.1.2.1](#).

e Unless an alternative monitoring schedule is agreed by the Investigator and UCB responsible physician. Determination of stabilization is at the discretion of the Investigator in consultation with the hepatologist (as applicable) and UCB responsible physician, as needed.

### **12.2.1.1 Consultation with Medical Monitor and local hepatologist**

Potential drug-induced liver injury events require notification of the Medical Monitor within 24 hours (eg, by laboratory alert), and the subject must be discussed with the Medical Monitor as soon as possible. If required, the subject must also be discussed with the local hepatologist. The local hepatologist is the expert usually consulted by the treating physician for assessment and management of potential hepatic disease. This would usually be a hepatologist but may be a gastroenterologist. If determined necessary, this discussion should be followed by a full hepatology assessment (see [Section 12.2.1.3](#)) and SAE report (if applicable).

### **12.2.1.2 Immediate action: determination of IMP discontinuation**

All PDILI events require immediate action, testing, and monitoring.

The immediate action is dependent on the laboratory values and symptoms of hepatitis or hypersensitivity and ranges from continuation of IMP (followed by immediate investigation) to immediate and permanent discontinuation (see [Section 6.3.1](#) and [Table 12-3](#) for details).

When IMP is discontinued, all concomitant medications and herbal supplements that are not medically necessary should also be discontinued. The Investigator should also consider dose reduction for medically necessary concomitant medication and consider changing any medically required concomitant medication known to be hepatotoxic to a suitable alternative.

#### **12.2.1.2.1 IMP restart/rechallenge**

Subjects who are immediately discontinued from IMP due to having met certain criteria for PDILI (as described in [Section 6.3.1](#) and [Table 12-3](#)), but for whom an alternative diagnosis is confirmed, ie, drug-induced liver injury is excluded, can rarely restart IMP. Rechallenge with IMP can occur only if ALL of the following requirements are met at the time of the rechallenge:

- The results of additional testing and monitoring described in [Section 12.2.1.3](#) and [Section 12.2.1.4](#) confirm a nondrug-related cause for the abnormal hepatic laboratory parameters and any associated symptoms (ie, a subsequent alternative diagnosis fully explains the hepatic findings).
- No alternative treatment options are available to the subject.
- The subject has shown clear therapeutic benefit from the IMP.
- Subject's ALT or AST elevations do not exceed  $\geq 3\times\text{ULN}$ .
- Subject's total bilirubin is  $< 1.5\times\text{ULN}$ .
- Subject has no signs or symptoms of hypersensitivity.
- The rechallenge is approved by the UCB responsible physician and a hepatologist. The hepatologist must be external to UCB. It is recommended that the hepatologist be a local hepatology expert or the hepatologist treating the subject.
- Subject agrees to the investigator-recommended monitoring plan and understands their individual benefit risk for restarting IMP and this is adequately documented.

---

### **12.2.1.3 Testing: identification/exclusion of alternative etiology**

The measurements and additional information required for the assessment of PDILI events when there is a reasonable possibility that they may have been caused by the IMP are detailed in [Table 12-4](#) (laboratory measurements) and [Table 12-5](#) (additional information). Results of the laboratory measurements and information collected are to be submitted to the Sponsor on the corresponding eCRF. If the medical history of the subject indicates a requirement for other assessments not included below, these additional assessments should be completed and submitted, as applicable.

All blood samples should be stored, if possible. If tests are done locally for more rapid results, a concurrent sample must also be sent to the central laboratory.

The following measurements are to be assessed:

**Table 12-4: PDILI laboratory measurements**

Virology-related	Hepatitis A IgM antibody
	HBsAg
	Hepatitis E IgM antibody
	HBcAb-IgM
	Hepatitis C RNA
	Cytomegalovirus IgM antibody
	Epstein-Barr viral capsid antigen IgM antibody (if unavailable, obtain heterophile antibody or monospot testing)
Immunology	Anti-nuclear antibody (qualitative and quantitative)
	Anti-smooth muscle antibody (qualitative and quantitative)
	Type 1 anti-liver kidney microsomal antibodies (qualitative and quantitative)
Hematology	Eosinophil count
Urinalysis	Toxicology screen a
Chemistry	Amylase
	Sodium, potassium, chloride, glucose, BUN, creatinine
	Total bilirubin, ALP, AST, ALT, GGT, total cholesterol, albumin
	If total bilirubin $\geq 1.5 \times$ ULN, obtain fractionated bilirubin to obtain % direct bilirubin
	Serum CPK and LDH to evaluate possible muscle injury causing transaminase elevation
Additional	Prothrombin time/INR b
	Serum pregnancy test
	PK sample

ALP= alkaline phosphatase; ALT=alanine aminotransferase; AST= aspartate aminotransferase; BUN=blood urea nitrogen; CPK=creatine phosphokinase; GGT=gamma-glutamyltransferase; HBcAb-IgM=hepatitis B core antibody-IgM; HBsAg=hepatitis B surface antigen; IgM=immunoglobulin M; INR=international normalized ratio; LDH=lactate dehydrogenase; PDILI=potential drug-induced liver injury; PK=pharmacokinetic; RNA=ribonucleic acid; ULN=upper limit of normal

a For detecting substances (ie, amphetamines, benzodiazepines, opioids, marijuana, cocaine, phencyclidine, and tricyclic antidepressants), additional tests may be performed based on the Investigator's medical judgment and subject's history.

b Measured only for subjects with ALT  $>8 \times$ ULN, elevations in total bilirubin, and symptoms of hepatitis or hypersensitivity. Hepatitis symptoms include fatigue, nausea, vomiting, and right upper quadrant pain or tenderness; hypersensitivity symptoms include eosinophilia ( $>5\%$ ), rash, and fever (without clear alternative cause).

Additional information to be collected is presented in [Table 12-5](#).

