### **6.3.1 Potential drug-induced liver injury IMP discontinuation criteria**

Subjects with potential drug-induced liver injury (PDILI) must be assessed to determine if IMP must be discontinued. In addition, all concomitant medications and herbal supplements that are not medically necessary should also be discontinued.

The PDILI criteria below require immediate discontinuation of IMP:

- Subjects with either of the following:
  - ALT or AST  $\geq 8$ xULN
  - ALT or AST  $\geq 3$ xULN and coexisting total bilirubin  $\geq 2$ xULN
  - Subjects with ALT or AST  $\geq 3$ xULN who exhibit temporally associated symptoms of hepatitis or hypersensitivity. Hepatitis symptoms include fatigue, nausea, vomiting, right upper quadrant pain or tenderness. Hypersensitivity symptoms include fever (without clear alternative cause), rash, or eosinophilia (ie,  $>5\%$ ).

If a nondrug-related cause for the symptoms can be confirmed, these subjects may resume IMP administration after discussion with the responsible UCB physician, but only when the requirements for rechallenge with IMP as provided in [Section 12.2.1.2.1](#) are followed.

The PDILI criterion below allows for subjects to continue on IMP at the discretion of the Investigator.

- Subjects with ALT or AST  $\geq 5$ xULN and  $<8$ xULN, total bilirubin  $<2$ xULN, and no eosinophilia (ie,  $\leq 5\%$ ), with no fever, rash, or symptoms of hepatitis (eg, fatigue, nausea, vomiting, right upper quadrant pain or tenderness).

Evaluation of PDILI must be initiated as described in [Section 12.2.1](#) with repeat tests performed in 2 weeks. Upon retest, if ALT or AST values have reduced to  $<5$ xULN, the subject can continue with the study. However, if ALT or AST remains  $\geq 5$ xULN  $<8$ xULN after retest, IMP should be temporarily withheld and subject should undergo a repeat test in 2 weeks. The subject will continue to be monitored at least twice per week until values normalize, stabilize, or return to within baseline values. If ALT or AST values remain  $\geq 5$ xULN even after the second retest, then the subject should be permanently withdrawn from the study and should be followed for possible PDILI.

If subjects are unable to comply with the applicable monitoring schedule, IMP must be discontinued immediately.

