### 12.1.1.3 Adverse events of special interest

An AE of special interest is any AE that a regulatory authority has mandated be reported on an expedited basis, regardless of the seriousness, expectedness, or relatedness of the AE to the administration of a UCB product/compound.

Potential Hy's Law, defined as  $\geq 3 \times \text{ULN}$  ALT or AST with coexisting  $\geq 2 \times \text{ULN}$  total bilirubin in the absence of  $\geq 2 \times \text{ULN}$  ALP, with no alternative explanation for the biochemical abnormality, must ALWAYS be reported to UCB as an AE of special interest (ie, without waiting for any additional etiologic investigations to have been concluded). Follow-up information should then be reported if an alternative etiology is identified during investigation and monitoring of the subject.

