**Table 12-2: Laboratory measurements**

Hematology	Biochemistry	Urinalysis
Basophils	Calcium	pH
Eosinophils	Chloride	Albumin (protein)
Lymphocytes	Magnesium	Glucose
Monocytes	Potassium	Blood
Neutrophils	Sodium	Leukocyte esterase
Hematocrit	Glucose	Nitrite
Hemoglobin	BUN	Urine dipstick for pregnancy testing b
MCH	Creatinine	Urine drug screen c
MCHC	hs-CRP	
MCV	AST	
Platelet count	ALT	
RBC count	GGT	
WBC count	ALP	
	Total bilirubin	
	Triglycerides a	
	Cholesterol a	
	HDL cholesterol a	
	LDL cholesterol a	
	LDH	
	Serum pregnancy testing b	

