### 12.2.1 Evaluation of potential drug-induced liver injury

The PDILI IMP discontinuation criteria for this study are provided in [Section 6.3.1](#), with the accompanying required follow-up investigation and monitoring detailed below. All PDILI events must be reported as AEs and PDILI events meeting SAE criteria should be reported to the Sponsor within 24 hours of learning of their occurrence. Any PDILI event that meets the criterion for potential Hy's Law must be reported within 24 hours of learning of their occurrence as an AE of special interest (see [Section 12.1.1.3](#)), and, if applicable, also reported as an SAE (see [Section 12.1.1.2](#)).

Evaluation of PDILI consists of the diagnostic testing and continued monitoring included in [Table 12-3](#) (specific tests dependent on laboratory results and corresponding symptoms) and consultation with a local hepatologist (if applicable; discussed in [Section 12.2.1.1](#)). The local hepatologist is the expert usually consulted by the treating physician for assessment and management of potential hepatic disease. This would usually be a hepatologist but may be a gastroenterologist. Additional investigation and monitoring may be required and adapted based on the diagnosis after the cause of the liver injury/abnormality is confirmed (details in [Section 12.2.1.4](#)).

The results of all monitoring, including laboratory testing and other testing, should be made available to the study site and Sponsor.

All initial tests resulting in abnormal hepatic laboratory values need to be repeated, but appropriate medical action must not be delayed waiting for the repeat result.

If tests are done locally for more rapid results, a concurrent sample should also be sent to the central laboratory whenever possible. Medical care decisions are to be made initially using the most rapidly available results and a conservative approach must be taken if the results from the 2 laboratory tests are significantly different. Data from the local and central laboratory are to be recorded on the applicable eCRF pages.

When IMP is discontinued, all concomitant medications and herbal supplements that are not medically necessary should also be discontinued. In these cases, the Investigator should also consider dose reduction for medically necessary concomitant medication and consider changing

---

any medically required concomitant medication known to be hepatotoxic to a suitable alternative.

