**Table 12–3: Required investigations and follow-up for PDILI**

Laboratory value		Symptoms a of hepatitis or hypersensitivity	Immediate		Follow up	
ALT or AST	Total bilirubin		Consultation requirements	Actions	Testing	Evaluation
≥3xULN	≥2xULN b	NA	Hepatology consult c Medical Monitor must be notified within 24 hours (eg, by laboratory alert) and subject discussed with Medical Monitor ASAP.	Immediate IMP discontinuation. d	Essential: Must have repeat liver chemistry values and additional testing completed ASAP (see Section 12.2.1.3 ); recommended to occur at the site with HCP.	Monitoring of liver chemistry values at least twice per week until values normalize, stabilize, or return to within baseline values. e
≥3xULN	NA	Yes				
≥8xULN	NA	NA				

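### Table 12-4 footnote b restricts PT/INR more narrowly than the protocol's own immediate-stop liver criteria, so some potential Hy's Law events would go without it

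*Protocol*

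**What the plan says.** Protocol Table 12-4 lists prothrombin time/INR among the measurements for potential drug-induced liver injury (PDILI), subject to footnote b. The footnote opens "Measured only for subjects with ALT" above 8xULN and continues with "elevations in total bilirubin, and symptoms of hepatitis or hypersensitivity". AST is not mentioned, and no cut-off is given for the bilirubin elevation.

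Section 6.3.1 introduces its list with "The PDILI criteria below require immediate discontinuation of IMP". The criteria are alternatives, and rows 1 to 3 of Table 12-3 repeat them:

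- row 1: ALT or AST at least 3xULN with total bilirubin at least 2xULN;
- row 2: ALT or AST at least 3xULN with symptoms of hepatitis or hypersensitivity;
- row 3: ALT or AST at least 8xULN.

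For all three rows the testing column reads "Must have repeat liver chemistry values and additional testing completed ASAP" and points to Section 12.2.1.3, which contains Table 12-4.

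Section 12.1.1.3 defines potential Hy's Law as ALT or AST at least 3xULN with bilirubin at least 2xULN, without ALP at least 2xULN and with no alternative explanation. Such an event "must ALWAYS be reported to UCB as an AE of special interest". The definition requires neither symptoms nor ALT above 8xULN.

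Section 12.2.1 says in advance that the work-up is conditional: "specific tests dependent on laboratory results and corresponding symptoms".

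**The concern.** Attaching a condition to a test is not a fault, and leaving PT/INR out of the asymptomatic row from 5xULN to below 8xULN is defensible. The difficulty is that the condition chosen does not match the events the protocol itself treats as most serious. Those are defined by alternatives on either transaminase. The footnote asks for a conjunction on ALT only.

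A site following the footnote literally would not measure clotting in many events that stop study drug immediately, including potential Hy's Law events. The routine panel in Table 12-2 contains no coagulation test to fall back on. A site that took the list as alternatives would test a different set of subjects, so the liver work-up could differ between sites for reasons unrelated to the patients.

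**Working it through.** The protocol gives no figure to reproduce here. The check is a comparison of rules.

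**Individual cases.** Each meets an immediate-stop criterion and the Hy's Law transaminase and bilirubin pattern, and each fails footnote b as written:

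- ALT 5xULN, bilirubin 3xULN: fails because ALT is not above 8xULN.
- ALT 10xULN, bilirubin 3xULN, no symptoms: fails on symptoms.
- AST 12xULN, ALT 6xULN, bilirubin 3xULN, with symptoms: fails because the footnote looks only at ALT.

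**Coverage grid.** ALT and AST each take five levels (below 3, 3 to below 5, 5 to below 8, exactly 8, above 8, all xULN). Bilirubin takes three (normal, above ULN to below 2xULN, at least 2xULN). Symptoms are yes or no. Because the footnote gives no bilirubin cut-off, an elevation is taken as anything above ULN. That makes 5 × 5 × 3 × 2 = 150 patterns.

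- Row 1: 24 of the 25 ALT/AST pairs have a maximum of at least 3xULN, so 24 × 1 × 2 = 48 patterns. As written, PT/INR needs ALT above 8xULN (5 pairs) and symptoms: 5 patterns. The 43 missed are 19 pairs with ALT at or below 8xULN × 2 = 38, plus 5 with ALT above 8xULN but no symptoms.
- Row 2: 24 × 3 × 1 = 72 patterns. As written: 5 pairs × 2 raised-bilirubin levels = 10.
- Row 3: 16 pairs reach at least 8xULN, so 16 × 3 × 2 = 96 patterns. As written: 10. If the list is read as alternatives, the patterns missed are those with ALT not above 8xULN, normal bilirubin and no symptoms: 16 − 5 = 11, leaving 85 covered.
- Rows 1 to 3 combined: the 96 in row 3, plus 8 pairs with a maximum from 3xULN to below 8xULN × 4 bilirubin/symptom combinations that qualify = 32. Total 128.
- Row 4 (5xULN to below 8xULN, bilirubin below 2xULN, no symptoms): 5 pairs × 2 = 10 patterns.

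| Table 12-3 | Patterns | As written (all three) | Read as alternatives | Proposed wording |
|---|---|---|---|---|
| Row 1 (Hy's Law pattern) | 48 | 5 | 48 | 48 |
| Row 2 | 72 | 10 | 72 | 72 |
| Row 3 | 96 | 10 | 85 | 96 |
| Rows 1–3 combined | 128 | 10 | 117 | 128 |
| Row 4 | 10 | 0 | 5 | 0 |

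Row 1 stands for the Hy's Law pattern before its ALP and alternative-explanation conditions are applied.

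**Second grid.** A different set of values that also applies the ALP condition has 7 ALT × 7 AST × 4 bilirubin × 2 ALP × 2 symptom levels = 784 points. As written, PT/INR is triggered in 708 − 624 = 84 of 708 immediate-stop profiles and 192 − 164 = 28 of 192 potential Hy's Law profiles. Read as alternatives, 38 of 708 and 0 of 192 are missed. The percentages shift with the grid; the direction does not.

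**The case against.** The strongest reply is that the footnote was meant as a list of three groups. Its three items (high ALT, raised bilirubin, symptoms) roughly track the three triggers in Table 12-3, and on that reading no Hy's Law pattern is missed. That reading is possible, but it sits badly with a restriction that says *only* and joins its items with *and*. It also does not fully repair the footnote. AST at least 8xULN without a qualifying ALT, and ALT of exactly 8xULN, remain uncovered when bilirubin is normal and there are no symptoms.

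It can also be said that no protocol text requires PT/INR in every immediate-stop event, and that no decision depends on it: discontinuation, Hy's Law reporting and rechallenge rest on transaminases, bilirubin, ALP, symptoms or an alternative diagnosis. This is correct, and it limits the consequence.

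Finally, other protection exists. Rows 1 to 3 bring a hepatology consult, Medical Monitor notification within 24 hours, repeat chemistry and monitoring at least twice weekly. The unrestricted chemistry panel ("Total bilirubin, ALP, AST, ALT, GGT, total cholesterol, albumin") includes albumin. A hepatologist may well order an INR. None of this requires one, however. The sentence in Section 12.2.1.3 allowing further assessments depends on medical history and concerns tests not already listed, whereas PT/INR is listed and expressly restricted.

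**Conclusion.** The concern holds. As written, footnote b is much narrower than the immediate-discontinuation criteria (10 of 128 patterns covered) and leaves out PT/INR in most potential Hy's Law patterns (43 of 48 missed). On the more generous reading the Hy's Law gap closes and 11 of 128 patterns, all in row 3, remain uncovered. Either way the footnote needs correcting.

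The counts are unweighted and depend on the cut-points chosen. They describe how far the rules overlap, not how many subjects would be affected. The protocol states no PDILI rate, so that number cannot be given. The analysis also assumes that a bilirubin elevation means above ULN.

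This is a patient-safety wording point that should be fixed. It does not touch the efficacy analysis, and its clinical consequence is limited by the consult and repeat testing already required.

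**What to change.** Replace footnote b with: *Measured for subjects with ALT or AST ≥8xULN, OR ALT or AST ≥3xULN with total bilirubin ≥2xULN, OR ALT or AST ≥3xULN with symptoms of hepatitis or hypersensitivity.* The footnote's existing list of symptoms can stay.

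This repeats the three criteria of Section 6.3.1 and Table 12-3, so coverage of rows 1 to 3 is complete by construction (128 of 128). It brings in AST, replaces >8 with ≥8 and removes the ambiguity. The asymptomatic row from 5xULN to below 8xULN needs no change.

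The cost is one footnote and one additional blood test, already on the PDILI list, in events that already stop study drug and require prompt further testing.

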**Table 12-5: PDILI information to be collected**

New or updated information
Concomitant prescription and over-the-counter medications (eg, acetaminophen, herbal remedies, vitamins); dosages and dates should be included.
Pertinent medical history, including the following: 

History of liver disease (eg, autoimmune hepatitis, nonalcoholic steatohepatitis or other “fatty liver disease”)

Adverse reactions to drugs

Allergies

Relevant family history or inheritable disorders (eg, Gilbert’s syndrome, alpha-1 antitrypsin deficiency)

Recent travel

Progression of malignancy involving the liver (Note: Metastatic disease to the liver, by itself, should not be used as an explanation for significant AST and/or ALT elevations.)

The appearance or worsening of clinical symptoms of hepatitis or hypersensitivity (eg, fatigue, nausea, vomiting, right upper quadrant pain or tenderness, decreased appetite, abdominal pain, jaundice, fever, or rash)
Recent clinically significant hypotension or hypoxemia with compromised cardiopulmonary function
Alcohol and illicit drug use
Results of liver imaging or liver biopsy, if done
Results of any specialist or hepatology consult, if done
Any postmortem/pathology reports

ALT=alanine aminotransferase; AST=aspartate aminotransferase; PDILI=potential drug-induced liver injury

#### **12.2.1.4 Follow-up evaluation**

Potential drug-induced liver injury events require follow-up monitoring as described in [Table 12-3](#). Monitoring should continue until liver chemistry values normalize, stabilize, or return to baseline. Determination of stabilization is at the discretion of the Investigator in consultation with the hepatologist (as applicable) and UCB responsible physician, as needed.

